7.5.2 ECGs in Part B

In Part B, ECGs will be collected on Day -1, at pre-dose on Days 2, 7, 14, 21, and 29, at post-dose on Day 1 (4 hours) and Day 28 (1, 4, and 8 hours), during follow-up on Days 35 and 42 or 56. The same parameters reported in Part A will also be reported for Part B.

7.5.2.1 ECGs over time in Part B

At each time point, the change from baseline will be derived for each numeric parameter using the Day -1 value as baseline. Descriptive statistics for the value of each parameter at each time point and the change from baseline for each parameter at each post-dose time point will be provided by treatment group.

Plots of the mean \pm standard error for each vital sign, collected while supine, over time (baseline through Day 56) will be provided by treatment group.

The single tracing collected on the Day -2 will be included in by-subject listings but will not be included in any summary tables.

7.5.2.2 Clinically Significant ECGs in Part B

The number (percent) of subjects who either had an abnormal ECG (regardless whether clinically significant or not) or had a clinically significant change in the QT_{cf} value while on-treatment will be tabulated by treatment group. Abnormal QT_{cf} values will be determined using the following criteria:

- $QT_{cf} \geq 480$ msec
- $QT_{cf} \geq 500$ msec
- $QT_{cf} \geq 550$ msec
- Change from baseline in $QT_{cf} \geq 30$ msec
- Change from baseline in $QT_{cf} \geq 60$ msec.

All on-treatment values, including unscheduled assessments, will be considered, and the denominator for the percentages will be the number of subjects in the Safety Population.

All subjects who have an extreme QT_{cf} value or orthostatic value will be documented in a by-subject listing. The listing will include all of the ECG measurements from the study for the subject, and the noteworthy values will be flagged. A similar listing for the Part A will also be produced, but no summary table of the results is planned for Part A.

8 Pharmacokinetic Analyses

The PK analysis for the study will be detailed in a separate PK SAP.

9 Exploratory PK/PD and PK/Biomarker Analyses

The exploratory PK/PD and PK/biomarker analyses for the study will be detailed in a separate SAP.

10 Additional, non-PK, Analyses for the DDI study

Any additional non-PK analyses for the DDI study will be detailed in a separate SAP.

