7.2. Exclusion Criteria

Subjects will be excluded from study enrollment if they meet any of the following criteria at screening and/or enrollment:

- [1] are taking a statin, any PCSK9 medications, or have started taking other TG lowering agents (e.g., niacin, fish oils) within the last 3 months. Subjects on stable background (> 3 months) of non-statin TG lowering agents may be included in the study.
- [2] are investigator site personnel directly affiliated with this study or their immediate families. Immediate family is defined as a spouse, parent, child, or sibling, whether biological or legally adopted.
- [3] are Chorus (Lilly) or CRO-site employees.
- [4] are currently enrolled in a clinical trial involving an investigational product or off-label use of a drug or device, or are concurrently enrolled in any other type of medical research judged not to be scientifically or medically compatible with this study.
- [5] have participated (defined as last dose of study drug) in a clinical trial involving an investigational product or non-approved use of a drug within the last 30 days or within 5 half-lives, whichever is longer.

- [6] have an abnormality in the 12-lead ECG, including corrected QT (QTc) interval with Bazett's correction >450 msec for men and >470 msec for women or an abnormality that, in the opinion of the investigator, increases the risks associated with participating in the study. ECGs may be repeated after 5 minutes resting quietly if the subject's heart rate is >75 bpm.
- [7] have uncontrolled hypertension, or at screening a resting supine systolic BP of >150 mmHg or diastolic BP of >100 mmHg, confirmed after 5 minutes in the supine and resting state.
- [8] have any current or prior history of significant cardiovascular disease, including acute myocardial infarction, unstable angina, congestive heart failure, cardiomyopathy or cardiomypitis. Subjects with clinically significant arrhythmia, including but not limited to atrial fibrillation, supraventricular/ventricular tachycardia, atrial-ventricular block, or sick sinus syndrome should also be excluded. Subjects with asymptomatic sinus arrhythmia, sinus bradycardia, or mild sinus tachycardia may be enrolled.
- [9] show evidence of hepatitis C virus (HCV) and/or positive HCV antibody.
- [10] show evidence of hepatitis B virus and/or positive hepatitis B surface antigen.

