7.4.2.3 Clinically Significant Vital Sign Change in Part B

The number (percent) of subjects who experience either orthostatic hypotension or a clinically significant deviation in vital signs while on-treatment will be tabulated by treatment group. Vital sign normal are defined as follows:

- Pulse rate < 50 bpm or > 100 bpm,
- Systolic blood pressure either ≤ 90 mmHg or ≥ 160 mmHg,
- Diastolic blood pressure either ≤ 50 mmHg or ≥ 100 mmHg.

All on-treatment values, including unscheduled assessments, will be considered, and the denominator for the percentages will be the number of subjects in the Safety Population.

All subjects who have a clinically significant change in vital signs or orthostatic hypotension will be documented in a by-subject listing. The listing will include all of the vital sign measurements

from the study for the subject, and abnormal values will be flagged. A similar listing for the data from Part A will also be produced, but no a summary table of the results as are planned for Part A.

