7.5 Electrocardiograms

Subjects must be supine for at least 5 minutes prior to and remain awake during each 12-lead, digital, triplicate electrocardiogram (ECG) collection. ECGs will be read by a qualified physician at the site to document parameter measurements and to determine any clinically relevant findings. The triplicate numeric measurements will be averaged at each time point to obtain the value that will be used for analyses, while the most severe interpretation (Normal; Abnormal, not Clinically Significant; Abnormal, Clinically Significant) among the triplicate measurements will be used for analyses. However, all abnormalities documented on any of the triplicate measurements will be reported in the listings. The investigator, or qualified designee, will report any new clinically relevant finding from any of the triplicate measurements as an AE.

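### Part B counts of abnormal ECG interpretations and of pulse and blood-pressure limits are not split by baseline status, so stable pre-existing findings are counted as on-treatment findings

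*SAP*

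**What the plan says.** Two Part B tables count ECG and vital-sign outliers on treatment.

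- **ECG (SAP 7.5.2.2).** The table takes subjects "who either had an abnormal ECG (regardless whether clinically significant or not"). The other way into the table is to meet a QTcF criterion during treatment. Five QTcF criteria follow: three absolute limits (480, 500 and 550 msec or more) and two changes from baseline (30 and 60 msec or more). SAP 7.5 adds that at each time point "the most severe interpretation (Normal; Abnormal, not Clinically Significant; Abnormal, Clinically Significant) among the triplicate measurements will be used for analyses". On scope and denominator: "All on-treatment values, including unscheduled assessments, will be considered, and the denominator for the percentages will be the number of subjects in the Safety Population".
- **Vital signs (SAP 7.4.2.3).** The table takes subjects "who experience either orthostatic hypotension or a clinically significant deviation in vital signs while on-treatment". The pulse and pressure criteria are absolute: pulse below 50 or above 100 bpm, systolic pressure 90 or lower or 160 or higher, diastolic pressure 50 or lower or 100 or higher (mmHg).
- **Entry.** Protocol 7.2, exclusion [8], states: "Subjects with asymptomatic sinus arrhythmia, sinus bradycardia, or mild sinus tachycardia may be enrolled". Protocol 7.1, inclusion [9], requires systolic pressure below 150 and diastolic below 100 mmHg and gives no lower limit.
- **Baseline elsewhere.** SAP 7.5.2.1 summarises change from Day -1 for numeric ECG parameters. SAP 7.4.2.1 summarises change from Day 1 for supine vital signs. SAP 7.3.2.2 plans baseline shift tables for laboratory data. No such table is planned for ECG interpretation or for the pulse and blood-pressure limits.

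**The concern.** The section headings speak of clinically significant ECGs and of vital-sign change. The interpretation count, however, takes any grade of abnormality, and the pulse and pressure counts take any value beyond a limit, whether or not it was there before the first dose. A subject enrolled with a stable pulse of 48 bpm and an ECG read as sinus bradycardia enters both tables at whatever dose was assigned.

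The SAP is stricter elsewhere. An adverse event must emerge or worsen after the first dose to be summarised (SAP 7.2), and laboratory categories are cross-tabulated against baseline. ECG interpretation has no summarised baseline comparison at all, because the changes in SAP 7.5.2.1 cover only numeric parameters.

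Safety is the primary objective, and these tables will be read by dose. In a group of 8, one subject is 12.5 percentage points. If carriers of stable findings fall unevenly across groups, the table can suggest a dose pattern that is not there or mask one that is.

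**Working it through.** The plan states no figure for these tables, and Part B has no power calculation, so there is nothing to reproduce. The check has two parts.

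**1. Each criterion against baseline and entry rules**

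| Criterion | Uses pre-treatment baseline? | Can a carrier be enrolled? |
|---|---|---|
| Abnormal ECG interpretation | No | Yes, at least the sinus findings in exclusion [8] |
| QTcF ≥480, ≥500, ≥550 msec | No | Hardly (see below) |
| QTcF change ≥30, ≥60 msec | Yes | Not applicable |
| Pulse <50 or >100 bpm | No | Yes, exclusion [8] |
| Systolic ≤90, diastolic ≤50 mmHg | No | Yes, no lower entry limit |
| Systolic ≥160, diastolic ≥100 mmHg | No | No, inclusion [9] |

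For QTcF, exclusion [6] bars a Bazett QTc above 450 msec in men and 470 msec in women. Since QTcF = QTcB × RR^(1/6), with RR in seconds, a subject exactly at the entry limit reaches 480 msec only if RR is at least (480/limit)^6:

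- Men: (480/450)^6 = 1.473 s, a heart rate of 60/1.473 = 40.7 bpm or lower.
- Women: (480/470)^6 = 1.135 s, a heart rate of 60/1.135 = 52.9 bpm or lower.

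At 60 bpm or more, QTcF cannot exceed QTcB.

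**2. Size of the effect with no drug effect**

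Inputs: 4 cohorts of 8 active and 2 placebo (SAP 1.3), so 8 subjects per dose and 4 × 2 = 8 pooled placebo. The prevalence p of a stable pre-existing flagged finding is an assumption; the documents give none. Each carrier is assumed to be flagged at least once on treatment. For a persistent ECG finding that is reasonable, because SAP 7.5.2 lists 9 on-treatment time points: Day 1 at 4 h (1), pre-dose on Days 2, 7, 14, 21 and 29 (5), and Day 28 at 1, 4 and 8 h (3).

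- Expected carriers per group: 8p.
- Chance of at least one in a group: 1 − (1 − p)^8. For p = 0.10 this is 1 − 0.9^8 = 1 − 0.430 = 0.570.
- Chance that two groups differ by 2 or more subjects (25 percentage points or more): the sum of P(X = a)·P(Y = b) over |a − b| ≥ 2, with X and Y independent binomial (8, p).

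| Assumed p | Expected per group | At least one in a group | Two groups differ by ≥2 |
|---|---|---|---|
| 5% | 0.4 | 34% | 8% |
| 10% | 0.8 | 57% | 19% |
| 20% | 1.6 | 83% | 34% |
| 30% | 2.4 | 94% | 41% |

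In a tabulation of new or worsened findings, subjects stable from baseline would add nothing to these counts.

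**The case against.** Counting every on-treatment value is a defensible, cautious choice in a first-in-human study. The tables are descriptive. A randomised placebo group enrolled under the same criteria should carry the same background on average. SAP 7.4.2.3 and 7.5.2.2 list all vital-sign or ECG measurements for each flagged subject. SAP 7.5 has any new clinically relevant ECG finding reported as an adverse event, and treatment-emergent events are tabulated by dose. With 8 subjects per dose, reading the listings is practical. Exclusion [6] can also be read as barring most ECG abnormalities, so 30% prevalence may be high.

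Most of this stands, and it limits the weight of the point. It does not remove it. Pooled placebo is only 8 subjects, so randomisation leaves chance imbalance, and a listing does not correct the summary beside it. Exclusion [8] shows that the sinus findings are admitted however [6] is read.

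A reader might infer that neither table uses baseline at all. That is wrong: two of the five QTcF criteria are changes from baseline. A reader might also infer that these are the only outlier counts. Orthostatic hypotension is also counted by time point in SAP 7.4.2.1, including Day 1 pre-dose, and at 4 hours post-dose in SAP 7.4.2.2. Nor do the documents support saying that a new abnormality could not be told from an old one: the listings and adverse event reporting allow it.

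**Conclusion.** The point holds for the ECG-interpretation count and for the absolute pulse and blood-pressure counts. In practice it bites on interpretation, pulse and low blood pressure, where carriers can be enrolled. It does not extend to the QTcF change criteria or to high systolic or diastolic pressure, and hardly to QTcF of 480 msec or more.

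Under an assumed prevalence of 10% to 30%, with each carrier flagged on treatment, a dose group has a 57% to 94% chance of at least one count unrelated to drug, and two groups have a 19% to 41% chance of differing by 25 percentage points or more. At 5% the figures are 34% and 8%. They scale with a prevalence that the documents do not supply.

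It would go too far to say that the tables measure enrolment rather than drug effect, given the concurrent placebo group and the change-from-baseline summaries. This is a cheap improvement to how safety data are displayed, not a defect that prevents new findings from being identified.

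**What to change.** Keep the planned all-values counts, the limits and the by-subject listings as they are. Replacing the counts with new findings only would lose a subject who is already beyond a limit before dosing and then moves further out. Add two displays:

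- **SAP 7.5.2.2:** a shift table by treatment group from the worst Day -1 triplicate interpretation to the worst on-treatment interpretation, with the categories normal, abnormal not clinically significant, and abnormal clinically significant. The layout can follow SAP 7.3.2.2, with worst on-treatment in place of the end-of-study visit.
- **SAP 7.4.2.3:** for each pulse and blood-pressure limit, next to the all-values count, the number of subjects who met it on treatment but not at Day 1 pre-dose.

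Day -1 ECGs and Day 1 pre-dose vital signs are already collected. The cost is a short SAP addition, a little more programming and one or two more tables. One limitation should be footnoted: a finding that comes and goes, and happens to be absent at the baseline reading, will still appear as new.
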